AP	serum alkaline phosphatase
ASEAN	Association of Southeast Asian Nations
AST	aspartate aminotransferase
AUC	area under the plasma concentration-time curve
$AUC_{0-\infty}$	area under plasma concentration vs time curve extrapolated to infinite time
AUC_{0-t}	area under plasma concentration versus time curve from administration to last observed concentration at time t
BE	bioequivalence
bpm	beats per minute
BPOM	Badan Pengawasan Obat dan Makanan (the Indonesian National Agency of Drug and Food Control, NA-DFC)
BQL	below quantification limit
C_{max}	maximum observed plasma concentration
CIs	confidence intervals
CPMP	Committee for Proprietary Medicinal Products
CRF	Case Report Form
CV	Coefficient of Variation
dL	decilitre

TERM	DEFINITION
ECG	electrocardiogram
e.g	example
EMA	European Medicines Agency
g	relative centrifugal force
GCP	Good Clinical Practice
GLP	Good Laboratory Practice
h, hr, hrs	hour(s)
K ₃ EDTA	tripotassium ethylenediaminetetraacetic acid
Hb	hemoglobin
HBsAg	Hepatitis B Surface Antigen
HCV	Hepatitis C Virus
HIV	Human Immunodeficiency Virus
HPLC-UV	high performance liquid chromatography with ultraviolet detector
ICF	Informed Consent Form
ICH	International Conference on Harmonisation
IEC	Independent Ethics Committee
IRB	Institutional Review Board
kg	kilogram
KGaA	Kommanditgesellschaft auf Aktien (limited partnership on shares)
kg/m ²	kilogram / square meter
L	litre
LLOQ	Lower Limit of Quantification
ln	natural logarithm with e constant
m, min, min(s)	minute(s)
mg	milligram
ms	millisecond(s)
mL	millilitre
mL/min	milliliter / minute(s)
mm	millimeter
mmHg	millimeter mercury column
n	number of subject

TERM	DEFINITION
ng	nanogram
ng/mL	nanogram / millilitre
NSAID	non-steroidal anti-inflammatory drug
PK	Pharmacokinetics
PT	Perseroan Terbatas (limited liability company)
QC	Quality Control
QTc	corrected QT interval
R	Comparator (Reference) drug
RBC	red blood cells
s, sec	second(s)
S ²	the error variance obtained from the ANOVA
SAE	Serious Adverse Event
SD	standard deviation
SOP	Standard Operating Procedure
SUSARs	suspected unexpected serious adverse reactions
T	Test drug
t _{0.1}	the t value for 90% CI
t _½	elimination half-life in plasma
Tbk	terbuka (public company)
t _{max}	time taken to reach maximum observed plasma concentration
ULN	upper limit of normal
USA	United States of America
v	the degree of freedom of the error variance from the ANOVA
Vd	volume of distribution
WBC	white blood cell (count)
WMA	World Medical Association
WOCBP	Women of Childbearing Potential
XR	extended release

1 SYNOPSIS

Study Title

A randomized, open-label, two-way crossover study assessing the bioequivalence (BE) between single dose of 750 mg Glucophage® XR Tablets (PT Merck Tbk, Jakarta, Indonesia-Manufactured) and 750 mg Glucophage® XR Tablets (Merck Santé, Semoy, France-Manufactured) under fasted state in healthy subjects

Protocol Number

- PPD [redacted] project code : PPD [redacted]
- Merck protocol number : MS200084_0015

Compound under investigation

Metformin

Objective

Primary objective:

- To assess bioequivalence between metformin hydrochloride (Glucophage® XR) manufactured in PT Merck Tbk, Indonesia (test drug) and metformin hydrochloride (Glucophage® XR) manufactured in Merck Santé, France (comparator drug) following single oral dose administration under fasting condition.

Secondary objective:

- To compare pharmacokinetic parameters of metformin after single dose administrations of test and comparator drugs.
- To examine the safety and tolerability of metformin after single dose administrations of test and comparator drugs.

Study Design

An open-label, randomized, single-dose, two-period, two-sequence crossover study under fasting conditions.

Study Subjects

Forty-eight (48) healthy adult male and female subjects, with at least 20% for each gender.

Dosing Regimen

- Test drug (T):
One (1) Glucophage® XR 750 mg Tablet produced by PT Merck Tbk, Indonesia given as a single oral dose with approximately 200 mL of water at ambient temperature after an overnight fast of at least 10 hours.
- Comparator / Reference drug (R):
One (1) Glucophage® XR 750 mg Tablet produced by Merck Santé, France of given as a single oral dose with approximately 200 mL of water at ambient temperature after an overnight fast of at least 10 hours.

Washout

At least 7 days between doses.

Duration of the Clinical Phase

The duration of the clinical phase (from Screening through Follow-Up Visit) will be approximately 6 weeks.

Inclusion Criteria:

1. Subject has provided written informed consent prior to the conduct of any study-related activities.
2. Male and female subjects.
3. Aged between 18 and 55 years, inclusive.
4. Body mass index of 18 to 25 kg/m².
5. Good physical and mental health status, determined on the basis of medical history and physical examination.
6. Vital signs (blood pressure, pulse rate, respiratory rate and body temperature) in sitting position within the normal range or showing no clinically relevant deviation per the Investigator's opinion.
7. All values for laboratory assessments (hematology, clinical chemistry and urinalysis) within the normal range or showing no clinically relevant deviation per the Investigator's opinion.
8. No clinically significant abnormality on 12-lead electrocardiogram (ECG) recording as judged by the Investigator; QTc (Bazett) should be ≤ 450 ms.
9. Non-smoker or smoker less than 10 cigarettes per day.
10. Women of childbearing potential (WOCBP) who are not nursing, are not pregnant, and are using highly effective methods of birth control (defined as those, alone or in combination, that result in a low failure rate (i.e., less than 1 percent per year) when used consistently and correctly) for a period of at least one month before and after dosing. Standard birth control methods are considered to be: oral or implanted contraceptive therapy and intra-uterine devices. Female subjects may also be enrolled if they are postmenopausal (i.e., at least 12 consecutive months of amenorrhea after the last menstrual period) or surgically sterilized/ hysterectomized at least 6 months prior to study participation.
11. WOCBP must have a negative urine pregnancy test at Screening and on each admission (Day 1 of each dosing period).
12. Negative screen for alcohol and drugs abuse (opiate class, barbiturates, cocaine and metabolites, amphetamines, cannabinoids and benzodiazepines) at Screening and on each Study Check-In (Day -1 of each dosing period).
13. Negative screen for Hepatitis B surface antigen (HBsAg), HCV antibodies and/or HIV antibodies.

Exclusion Criteria:

1. Participation in a clinical trial/study within 90 days prior to Screening.
2. Blood donation (equal or more than 300 mL) or significant blood loss within 90 days prior to first drug administration.
3. Any surgical or medical condition, including findings in the medical history or in the pre-study assessments, or any other significant disease, that in the opinion of the

investigator, constitutes a risk or a contraindication for the participation of the subject in the study or that could interfere with the study objectives, conduct or evaluation.

4. History of malignant diseases, except in-situ basal cell skin tumors treated with curative intent.
5. History of surgery of the gastrointestinal tract which could influence the gastrointestinal absorption and/or motility per the Investigator's opinion.
6. History or presence of relevant liver diseases or hepatic dysfunction (laboratory result for liver function test ≥ 1.5 ULN).
7. History or presence of renal failure or renal dysfunction based on clinical symptoms and finding (serum creatinine concentration >1.4 mg/mL).
8. Ascertained or presumptive hypersensitivity to the active drug substance and/or formulations' ingredients; history of anaphylaxis to drugs or allergic reactions in general, which the Investigator considers may affect the outcome of the study.
9. Receipt of any prescription or non-prescription medication within 14 days before the first drug administration, except for hormonal contraceptives in female, and including multivitamins and herbal products (e.g. St John's Wort).
10. Consumption of large quantities of methylxanthine-containing beverages (> 5 cups of coffee/day or equivalent).
11. Consumption of grapefruit, orange, cranberry or juices of these three fruits, 24 hours prior to drug administration.
12. Known lack of subject compliance or inability to communicate or cooperate with the Investigator (e.g., language problem, poor mental status).

Pharmacokinetic Sampling

- Eighteen (18) blood samples (1 x 10 mL and 17 x 5 mL) per subject in each period for drug content analysis.
- A 10-mL blood sample (control) will be drawn from fasting subjects immediately before drug administration.
- Subsequent blood samples are drawn 5 mL each at 1, 1.5, 2, 2.5, 3, 3.5, 4, 4.5, 5, 6, 7, 8, 10, 12, 16, 24, and 32 hours after drug administration.
- Subjects who complete both periods will have a total of 36 blood samples collected. Total blood volume collection is approximately 210 mL (including 10 mL for Screening, 10 mL pre-dose, 85 mL during each dosing period, and 10 mL for Follow-Up Visit).

Bioanalytical Sample Analyses

The metformin plasma concentrations will be measured using a validated high-performance liquid chromatography with ultraviolet detection (HPLC-UV; Waters™, Milford, MA, USA) and according to the bioanalytical laboratory's standard operating procedures and applicable regulatory requirements.

Pharmacokinetic Parameters

Pharmacokinetic parameters: AUC_{0-t} , AUC_{0-inf} , C_{max} , t_{max} , and $t_{1/2}$

Statistical Methods

- Pharmacokinetic analyses will be performed using standard non-compartmental methods of Phoenix® WinNonlin (PPD).
- The statistical method for testing bioequivalence is ANOVA for two-period, two-sequence, two-treatment cross-over comparing AUC_{0-t} and C_{max} after \ln transformation of the original values. The terms to be used in the ANOVA model are sequence, subject within sequence, period, and formulation. The t_{max} are compared using non-parametric test from the original data. The difference in t_{max} will be analyzed non-parametrically on the original data using Wilcoxon matched-pairs test. The $t_{1/2}$ difference will be analyzed using Student's paired t-test or Wilcoxon matched-pairs test depending whether the differences of the paired data were distributed normally or not.

Bioequivalence Criteria

Bioequivalence is concluded if the 90% confidence interval of the Test/Reference geometric means ratio is in the range of 80.00-125.00%, for AUC_{0-t} and C_{max} . This acceptance criterion is according to the Guideline on the Investigation of Bioequivalence, EMA, London, 2010; ASEAN Guideline for the Conduct of Bioequivalence Study, Lao PDR, 2015; and Indonesian guidelines, *Pedoman Uji Bioekivalensi, Badan Pengawas Obat dan Makanan (BPOM), Jakarta, 2015, page 37-38.*

Study Timeframe (TENTATIVE):

Apr – Jun 2018	Application for ethical clearance, BPOM approval, and analytical method verification
Jul 2018 – Aug 2018	Subject recruitment and blood sampling
Aug 2018 – Oct 2018	Analysis of drug concentrations and data management
Oct 2018 – Feb 2019	Statistical analysis and final study report.

2 PRODUCT BACKGROUND

2.1 Indication and Usage

Metformin hydrochloride extended release tablet is indicated for treatment of type 2 diabetes mellitus in adults, particularly in overweight patients, when dietary management and exercise alone does not result in adequate glycaemic control. Glucophage XR may be used as monotherapy or in combination with other oral antidiabetic agents, or with insulin. ⁽¹⁴⁾

2.2 Dosing Information

The usual starting dose of metformin hydrochloride extended release tablet is 500 mg once daily. After 10 to 15 days the dose should be adjusted on the basis of blood glucose measurements. A slow increase of dose may improve gastro-intestinal tolerability. The maximum recommended dose is 2000 mg XR once daily with the evening meal. If glycaemic control is not achieved on 2000 mg once daily, Glucophage XR 1000 mg twice daily should be considered, with both doses being given with food. If glycaemic control is still not achieved, patients may be switched to metformin IR tablets to a maximum dose of 3000 mg daily. In patients already treated with metformin tablets, the starting dose of Glucophage XR should be equivalent to the daily dose of metformin IR tablets. In patients treated with metformin at a dose above 2000 mg daily, switching to Glucophage XR is not recommended. ⁽¹⁴⁾

2.3 Pharmacokinetics

2.3.1 Absorption

After an oral dose of Glucophage XR 500, metformin absorption is significantly delayed compared to the immediate-release tablet (t_{max} at 2.5 hours) with a t_{max} at 7 hours. Following a single oral administration of 1500 mg of Glucophage XR 750, a mean peak plasma concentration of 1193 ng/mL is achieved with a median value of 5 hours and a range of 4 to 12 hours. Glucophage XR 750 was shown to be bioequivalent to Glucophage XR 500 at a 1500 mg dose with respect to C_{max} and AUC in healthy fed and fasted subjects. ⁽¹⁴⁾

Following a single oral administration in the fed state of one tablet of Glucophage XR 1000, a mean peak plasma concentration of 1214 ng/mL is achieved with a median time of 5 hours (range of 4 to 10 hours). Glucophage XR 1000 was shown to be bioequivalent to Glucophage XR 500 at a 1000 mg dose with respect to C_{max} and AUC in healthy fed and fasted subject. ⁽¹⁴⁾

At steady state, similar to the immediate-release formulation, C_{max} and AUC are not proportionally increased to the administrative dose. The AUC after a single oral administration of 2000 mg metformin prolonged-release is similar to that observed after administration of 1000 mg metformin immediate-release twice daily. ⁽¹⁴⁾

When two tablets of 500 mg metformin prolonged-release are administered in fed conditions the AUC is increased by approximately 70% (both C_{max} and t_{max} are only slightly increased). When the 1000 mg prolonged-release tablet are administered in fed conditions the AUC is increased by 77% (C_{max} is increased by 26% and t_{max} is slightly prolonged by about 1 hour). Metformin absorption from the prolonged-release formulation is not altered by meal composition. ⁽¹⁴⁾

No accumulation is observed after repeated administration of up to 2000 mg metformin prolonged-release. ⁽¹⁴⁾

2.3.2 Distribution

Plasma protein binding is negligible. Metformin partitions into erythrocytes. The blood peak is lower than the plasma peak and appears at approximately the same time. The red blood cells most likely represent a secondary compartment of distribution. The mean volume of distribution (Vd) ranged between 63-276 L. ⁽¹⁴⁾

2.3.3 Metabolism

Metformin is excreted unchanged in the urine. No metabolites have been identified in humans. ⁽¹⁴⁾

2.3.4 Elimination

Renal clearance of metformin is >400 mL/min, indicating that metformin is eliminated by glomerular filtration and tubular secretion. Following an oral dose, the apparent terminal elimination half-life is approximately 6.5 hours. When renal function is impaired, renal clearance is decreased in proportion to that of creatinine and thus the elimination half-life is prolonged, leading to increased levels of metformin in plasma. ⁽¹⁴⁾

2.4 Adverse Reactions

Common adverse reactions that reported in $\geq 1\%$ are gastrointestinal disorders (such as nausea, vomiting, diarrhoea, abdominal pain, and loss of appetite) and taste disturbance. ⁽¹⁴⁾

2.5 Contraindications

Metformin is contraindicated in patients with ⁽¹⁴⁾:

- Hypersensitivity to metformin or to any of the excipients
- Diabetic ketoacidosis, diabetic pre-coma
- Renal failure or renal dysfunction (creatinine clearance < 60 mL/min)
- Acute conditions with the potential to alter renal function such as dehydration, severe infection, shock, intravascular administration of iodinated contrast agents (see section Warning and Precaution)
- Acute or chronic disease which may cause tissue hypoxia such as: cardiac or respiratory failure, recent myocardial infarction, shock
- Elective major surgery (see section Warning and Precaution)
- Hepatic insufficiency, acute alcohol intoxication, alcoholism

2.6 Warning and Precaution

- Lactic acidosis is a rare, but serious (high mortality in the absence of prompt treatment), metabolic complication that can occur due to metformin accumulation. Reported cases of lactic acidosis in patients on metformin have occurred primarily in diabetic patients with significant renal failure. The incidence of lactic acidosis can and should be reduced by assessing also other associated risk factors such as poorly controlled diabetes, ketosis, prolonged fasting, excessive alcohol intake, hepatic insufficiency and any condition associated with hypoxia. The risk of lactic acidosis must be considered in the

event of non-specific signs such as muscle cramps with digestive disorders as abdominal pain and severe asthenia.

- As metformin is excreted by the kidney, it is recommended that creatinine clearance and/or serum creatinin levels be determined before initiating treatment and regularly thereafter.
- Decreased renal function in elderly subject is frequent and asymptomatic. Special caution should be exercised in situations where renal function may become impaired, for example when initiating antihypertensive therapy or diuretic therapy and when starting therapy with a non-steroidal anti-inflammatory drug (NSAID).
- The intravascular administration of iodinated contrast materials in radiologic studies can lead to renal failure. This may induce metformin accumulation and may expose to lactic acidosis. Therefore, depending on the renal function, metformin must be discontinued 48 hours before the test or from the time of the test and may be reinstated until 48 hours afterwards, and only after renal function has been re-evaluated and found to be normal.
- Metformin must be discontinued 48 hours before elective major surgery. Therapy may be restarted no earlier than 48 hours following surgery and only after renal function has been re-evaluated and found to be normal.
- All patients should continue their diet with a regular distribution of carbohydrate intake during the day. Overweight patients should continue their energy-restricted diet.
- The usual laboratory tests for diabetes monitoring should be performed regularly.
- Metformin alone does not cause hypoglycaemia, but caution is advised when it is used in combination with insulin or other oral antidiabetics (e.g., sulfonylureas or meglitinides).

2.7 Drug Interaction

- Depending on the renal function, metformin must be discontinued 48 hours before the test or from the time of the test and may not be reinstated until 48 hours afterward.
- The risk of lactic acidosis is increased in acute alcohol intoxication, particularly in case of fasting or malnutrition, hepatic insufficiency. Avoid consumption of alcohol and alcohol-containing medicinal product.
- More frequent blood glucose monitoring may be required when administered with medicinal product with intrinsic hyperglycaemic activity (e.g., glucocorticoids and tetracosactides (systemic and local routes), beta-2-agonists, danazol, chlorpromazine at high dosages of 100 mg per day and diuretics), especially at the beginning of treatment. If necessary, adjust the metformin dosage during therapy with the respective medicinal product and upon discontinuation.
- Co-administration with loop diuretics may increase the risk of lactic acidosis due to their potential to decrease renal function.
- Co-administration with ACE inhibitors may decrease the blood glucose levels. Therefore, dose adjustment of metformin may be necessary during and after addition or discontinuation of such medicinal products.

3 OBJECTIVE

The primary objective of this study:

- To assess bioequivalence between metformin hydrochloride (Glucophage® XR) manufactured in PT Merck Tbk, Indonesia (test drug) and metformin hydrochloride (Glucophage® XR) manufactured in Merck Santé, France (comparator drug) following single oral dose administration under fasting condition.

The secondary objective of this study:

- To compare pharmacokinetic parameters of metformin after single dose administrations of test and comparator drugs.
- To examine the safety and tolerability of metformin after single dose administrations of test and comparator drugs.

4 STUDY DESIGN

- Open-label, randomized, single-dose, two-period, two-sequence crossover study under fasting conditions (bioequivalence study design for metformin in accordance to *Indonesian guidelines, Pedoman Metodologi Uji Bioekivalensi Spesifik Zat Aktif, Badan Pengawas Obat dan Makanan (BPOM), Jakarta, 2015, page 39*).⁽⁴⁾
- Total subjects: Forty-eight (48) healthy adult male and female subjects, with at least 20% each gender.
- Total duration of the study (from Screening through Follow-Up Visit): approximately 6 weeks.
- Washout period: at least 7 days between doses.
- At Study Check-In, the subjects will report to the clinical site at least 12 hours prior to Day 1 dosing.
- Subjects will be required to stay for 32 hours after Day 1 dosing.

5 SUBJECT SELECTION

5.1 Number of Subjects

For this study, the total sample size will be 48 subjects.

5.2 Inclusion Criteria for Study Subjects

1. Subject has provided written informed consent prior to the conduct of any study-related activities.
2. Male and female subjects.
3. Aged between 18 and 55 years, inclusive.
4. Body mass index of 18 to 25 kg/m².
5. Good physical and mental health status, determined on the basis of medical history and physical examination.
6. Vital signs (blood pressure, pulse rate, respiratory rate and body temperature) in sitting position within the normal range or showing no clinically relevant deviation per the Investigator's opinion.

7. All values for laboratory assessments (hematology, clinical chemistry and urinalysis) within the normal range or showing no clinically relevant deviation per the Investigator's opinion.
8. No clinically significant abnormality on 12-lead electrocardiogram (ECG) recording as judged by the Investigator; QTc (Bazett) should be \leq 450 ms.
9. Non-smoker or smoker less than 10 cigarettes per day.
10. Women of childbearing potential (WOCBP) who are not nursing, are not pregnant, and are using highly effective methods of birth control (defined as those, alone or in combination, that result in a low failure rate (i.e., less than 1 percent per year) when used consistently and correctly) for a period of at least one month before and after dosing. Standard birth control methods are considered to be: oral or implanted contraceptive therapy and intra-uterine devices. Female volunteers may also be enrolled if they are postmenopausal (i.e., at least 12 consecutive months of amenorrhea after the last menstrual period) or surgically sterilized/ hysterectomized at least 6 months prior to study participation.
11. WOCBP must have a negative urine pregnancy test at Screening and on each Study Check-In (Day 1 of each dosing period).
12. Negative screen for alcohol and drugs abuse (opiate class, barbiturates, cocaine and metabolites, amphetamines, cannabinoids and benzodiazepines) at Screening and on each admission (Day 1 of each dosing period).
13. Negative screen for Hepatitis B surface antigen (HBsAg), HCV antibodies and/or HIV antibodies.

5.3 Exclusion and Restriction Criteria for Study Subjects

5.3.1 Exclusion Criteria

Any of the following criteria will exclude the subject from the study:

1. Participation in a clinical trial/study within 90 days prior to Screening.
2. Blood donation (equal or more than 300 mL) or significant blood loss within 90 days prior to first drug administration.
3. Any surgical or medical condition, including findings in the medical history or in the pre-study assessments, or any other significant disease, that in the opinion of the investigator, constitutes a risk or a contraindication for the participation of the subject in the study or that could interfere with the study objectives, conduct or evaluation.
4. History of malignant diseases, except in-situ basal cell skin tumors treated with curative intent.
5. History of surgery of the gastrointestinal tract which could influence the gastrointestinal absorption and/or motility per the Investigator's opinion.
6. History or presence of relevant liver diseases or hepatic dysfunction (laboratory result for liver function test \geq 1.5 ULN).
7. History or presence of renal failure or renal dysfunction based on clinical symptoms and finding (serum creatinine concentration $>$ 1.4 mg/mL).
8. Ascertained or presumptive hypersensitivity to the active drug substance and/or formulations' ingredients; history of anaphylaxis to drugs or allergic reactions in general, which the Investigator considers may affect the outcome of the study.

9. Receipt of any prescription or non-prescription medication within 14 days before the first drug administration, except for hormonal contraceptives in female, and including multivitamins and herbal products (e.g. St John's Wort).
10. Consumption of large quantities of methylxanthine-containing beverages (> 5 cups of coffee/day or equivalent).
11. Consumption of grapefruit, orange, cranberry or juices of these three fruits, 24 hours prior to drug administration.
12. Known lack of subject compliance or inability to communicate or cooperate with the Investigator (e.g., language problem, poor mental status).

This study will be carried out in accordance to the Good Clinical Practice (GCP) standards. Approval from the Ethics Committee will be sought prior to the conduct of the study.

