7 STUDY PROCEDURES

7.1 Screening

All assessments previously performed (within 21 days of the first study drug administration) may be used for enrollment purposes as long as a study-specific consent is signed prior to any other study-specific study procedure or assessment. During the Screening Visit the following will be completed:

- Informed consent for study
- Medical history (commencement of safety surveillance)
- Vital signs (blood pressure, pulse rate, respiratory rate, temperature)
- Physical examination and body measurements (height, weight)

- Clinical laboratory tests
 - Liver function : AP, ALT, AST, total protein, albumin and total/direct bilirubin
 - Renal function : serum creatinine and ureum
 - Hematology : hemoglobin, hematocrit, erythrocyte count, leucocyte count, and platelet count
 - Urinalysis : urine chemistry and urine sediment
 - Serology test : HBsAg, anti-HCV, and anti-HIV
 - Blood glucose
- Alcohol breath test and urine test for drug abuse (opiate class, barbiturates, cocaine and metabolites, amphetamines, cannabinoids and benzodiazepines)
- Pregnancy screening (female subjects only)
- 12-lead ECG (remain in a supine position)
- Eligibility (inclusion/exclusion criteria)

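### The creatinine limit of 1.4 in exclusion 7 does not match the protocol's own contraindication at a clearance below 60 mL/min, mainly in women, and no step calculates clearance

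*Protocol*

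**What the plan says.** - **The contraindication.** Protocol section 2.5 lists "Renal failure or renal dysfunction (creatinine clearance < 60 mL/min" among the conditions in which metformin must not be given.
- **The exclusion.** Exclusion 7 (synopsis, section 5.3.1 and SAP section 6) uses the same term: "History or presence of renal failure or renal dysfunction based on clinical symptoms and finding". It then gives one number, a serum creatinine above 1.4, without distinction by sex. The printed unit is mg/mL. SAP Tables 2 and 9 report creatinine in mg/dL, so I read the limit as 1.4 mg/dL; the unit is a separate correction.
- **The tests.** Screening (section 7.1) lists "Renal function : serum creatinine and ureum". The flow chart (Appendix C, footnote d) and SAP Tables 2 and 9 also list creatinine and ureum. None lists a clearance or an estimated filtration rate.
- **The precaution.** Section 2.6 says "it is recommended that creatinine clearance and/or serum creatinin levels be determined before initiating treatment", so serum creatinine alone satisfies it.
- **The judgement clauses.** Inclusion 7 requires laboratory values "within the normal range or showing no clinically relevant deviation per the Investigator's opinion". Exclusion 3 removes anyone with a finding that, in the investigator's opinion, "constitutes a risk or a contraindication for the participation of the subject in the study".

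**The concern.** The protocol states a numeric contraindication for its own drug and then screens on a different number. Serum creatinine translates into clearance differently by sex, age and (in some formulas) body weight. A single limit of 1.4 can therefore match 60 mL/min in some people and miss it in others.

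What is at stake is subject safety. Section 2.3.4 says that impaired renal function prolongs the half-life, "leading to increased levels of metformin in plasma", and healthy volunteers gain nothing from the drug to offset that. The exposure is limited to two single 750 mg doses at least 7 days apart.

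**Working it through.** The plan gives no figure to reproduce here. The check asks what clearance corresponds to the creatinine values that eligibility turns on.

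**Inputs from the documents.** Age 18 to 55 years and BMI 18 to 25 kg/m² (Protocol section 5.2); clearance limit 60 mL/min (section 2.5); creatinine limit 1.4 (section 5.3.1); normal creatinine 0.67–1.17 mg/dL in men and 0.51–0.95 mg/dL in women (SAP Table 2). So 1.4 is 1.4/0.95 = 1.47 times the female upper limit and 1.4/1.17 = 1.20 times the male one.

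**Assumed formulas.** The documents name none. Scr is serum creatinine in mg/dL.

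- Cockcroft-Gault, mL/min: (140 − age) × kg × (0.85 if female) / (72 × Scr). The weight at which it equals 60 is 60 × 72 × Scr / [(0.85 if female) × (140 − age)].
- CKD-EPI 2021, mL/min/1.73 m²: 142 × min(Scr/k, 1)^a × max(Scr/k, 1)^(−1.2) × 0.9938^age × (1.012 if female), with k = 0.7 and a = −0.241 for women, k = 0.9 and a = −0.302 for men. It is indexed to body surface area and section 2.5 is not, so the comparison with 60 is only approximate.

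**Step 1: at creatinine 1.4.** Example: woman aged 40, 60 × 72 × 1.4 / (0.85 × 100) = 71.2 kg.

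| Age | Woman: weight for Cockcroft-Gault 60 | Woman: CKD-EPI | Man: weight for Cockcroft-Gault 60 | Man: CKD-EPI |
|---|---|---|---|---|
| 18 | 58.3 kg | 55.9 | 49.6 kg | 74.7 |
| 40 | 71.2 kg | 48.8 | 60.5 kg | 65.2 |
| 55 | 83.7 kg | 44.4 | 71.2 kg | 59.4 |

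At the BMI ceiling of 25, a woman reaches 71.2 kg only at √(71.2/25) = 1.69 m and 83.7 kg only at √(83.7/25) = 1.83 m. A woman of 40 and 1.60 m at that ceiling weighs 64 kg and has a Cockcroft-Gault clearance of 100 × 64 × 0.85 / (72 × 1.4) = 54. There are counter-examples: a woman of 18 and 60 kg reaches 61.7. For men, indexed CKD-EPI falls below 60 only from age 54 (59.7).

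**Step 2: the creatinine at which the estimate equals 60.**

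- CKD-EPI: women 1.32 (18 years), 1.18 (40), 1.09 (55); men 1.50 (40), 1.39 (55).
- Cockcroft-Gault at 60 kg: woman 1.18 (40), 1.00 (55); man 1.39 (40), 1.18 (55).

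For women of 40 and 55 the two formulas agree closely (at 60 kg), and both place the matching creatinine well below 1.4.

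**Step 3: at the upper normal limit.** Cockcroft-Gault falls below 60 only at these weights:

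| Age | Woman at 0.95 | Man at 1.17 |
|---|---|---|
| 30 | under 43.9 kg | under 45.9 kg |
| 40 | under 48.3 kg | under 50.5 kg |
| 55 | under 56.8 kg | under 59.5 kg |

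For example, a woman of 55 and 45 kg has 85 × 45 × 0.85 / (72 × 0.95) = 47.5, and a man of 55 and 50 kg has 85 × 50 / (72 × 1.17) = 50.5. At mid-normal creatinine (0.73 and 0.92) the same two people pass, at 61.9 and 64.2. Indexed CKD-EPI gives no case below 60 at the upper normal limit; its lowest values, at age 55, are 70.8 (woman) and 73.6 (man).

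**The case against.** The case against is substantial.

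- **No required test is missing.** Section 2.5 is product background, and section 2.6 accepts serum creatinine. This stands. A reader might infer that the protocol omits a mandatory clearance measurement; the documents do not support that. Still, creatinine can only replace clearance if its cut-off corresponds to the clearance limit, and for most eligible women 1.4 does not.
- **Judgement already covers these people.** A woman at 1.4 is 47% above her normal limit, so inclusion 7 forces a decision, exclusion 3 names a contraindication, and exclusion 7 has its clinical wording. This also stands: being under 1.4 does not by itself admit anyone. But the investigator is given no calculated clearance with which to recognise the contraindication, and a printed limit of 1.4 can suggest that lower values are acceptable.
- **The formulas come from outside and differ.** This is right, and it limits the claim. A reader might infer that light volunteers with creatinine at the upper normal limit are contraindicated. Of the two formulas, only Cockcroft-Gault shows this, and only at low weight and mostly at older ages. For women near 1.4 the formulas largely agree.
- **The consequence is small.** Section 2.6 says reported lactic acidosis occurred primarily in diabetic patients with significant renal failure, and subjects stay on site for 32 hours after each dose. I accept this. It sets the weight of the point but does not reconcile the two limits.

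**Conclusion.** The point holds as a mismatch between two numbers in the same protocol. Exclusion 7 does not enforce the 60 mL/min contraindication, and nothing else in the plan does so by number.

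- **Women at 1.4:** most eligible women fall below 60 by Cockcroft-Gault and all do by indexed CKD-EPI (44 to 56).
- **Men at 1.4:** the mismatch is smaller, confined to lower weights by Cockcroft-Gault and to ages 54 and 55 by indexed CKD-EPI.
- **Between the upper normal limit and 1.4:** exclusion depends on investigator judgement.
- **At the upper normal limit:** the result depends on the formula and does not establish a gap by itself.

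This rests on the assumed formulas and on reading the limit as mg/dL. The documents do not show how many volunteers would be affected. The point concerns subject safety only: a reader might infer that the bioequivalence comparison is compromised, but nothing here supports that. It is an inexpensive improvement to consider, not a fault that invalidates the plan.

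**What to change.** In exclusion 7 (synopsis, Protocol section 5.3.1 and SAP section 6), add after the creatinine limit: *or estimated creatinine clearance < 60 mL/min (Cockcroft-Gault, from Screening age, sex, weight and serum creatinine)*. Record the value in the CRF. Cockcroft-Gault is proposed because it gives mL/min, the unit of the limit in section 2.5. Make the change in the same edit that corrects the creatinine unit.

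The cost is one clause of wording and one calculated CRF field. No new sample or visit is needed: creatinine is already measured, and Screening includes "Physical examination and body measurements (height, weight"). The downside is some additional screen failures, including small healthy volunteers with normal creatinine whom indexed CKD-EPI would pass. Section 11.3 plans to screen about twice the sample size, 2 × 48 = 96; whether that absorbs the extra failures cannot be shown from the documents.
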